6.1. Experimental design. This study employs a two-phase randomized clinical trial with 360 participants total across two sites (University of Florida and University of Arizona; 240 at the University of Florida and 120 at the University of Arizona). UF will be the parent site for the study. An initial cohort of 80 participants collected across the two sites will be assigned to one of four conditions as shown in Figure 2. Half of the recruited sample in Phase 1 will undergo CT; the other half will undergo training control (TC). The first interim analysis, to be performed when the first cohort of 80 completes 12-month follow-up (Phase 1), will investigate whether CT is significantly better than TC thereby enabling elimination of the TC condition. CT has previously been established with strong effects on cognitive and functional outcomes. If CT and TC are equally effective, groups will be collapsed at initiation of Phase 2 for planned assessment of adjunctive tDCS effects. If CT is more effective than TC, as previously shown, TC will be eliminated. Data from Phase 1 will also provide important mechanistic insight regarding neural mechanisms of CT vs. a well-matched education training control (TC). In Phase 2, the remaining 280 participants will be randomized to the two CT arms (i.e., eliminating the TC arms). After the remaining 280 participants have completed follow up in the CT arms (including those in Phase 1, total n=360) analyses will investigate the benefit of adjunctive administration of CT with tDCS. **Participants will be assessed at three primary time points: 1) baseline pre-training; 2) post-12 weeks of CT/TC + stimulation/sham; and 3) one year follow-up after all training (see Figure 3 for timeline).** This design will enable longitudinal analyses of CT and tDCS effects individually and in combination. We will examine CT and tDCS effects on cognitive performance, functional and metabolic neuroimaging measures, and everyday functional abilities. At each assessment, we will obtain clinical and medical history, neurocognitive measures, and neuroimaging (structural MRI, fMRI, MRS). All participants will undergo neuroimaging at baseline, following CT, and at one-year follow-up.

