6.2. Study participants and randomization procedure. We will recruit 240 older adults (women = 120; age: 65-89 years) at UF. Study participants will consist of healthy individuals who have expressed an interest in taking part in an intervention aimed at optimizing and possibly preserving cognitive functioning and brain health. Web-based permuted block randomization (with block size 8) will be used. In phase 1, each block will have two participants for each arm. In phase 2, each block will have four participants for each remaining arm. We will enroll people with evidence of age-related cognitive decline as defined by performance below the 80th percentile on the Cognitive Training assessment. People with pre-existing dementia, neurological brain disease, or who meet criteria for a diagnosis of mild cognitive impairment (MCI) will be excluded.

[figure not shown]
6.2.1. Experimental Design Considerations and Limitations: CT Approach. The POSITScience BrainHQ treatment program was selected because it 1) provides specific training tasks directed at three essential cognitive domains tied to our aims and hypotheses (attention, working memory, executive control) that correspond with the neurocognitive and functional neuroimaging measures to be studied; 2) is shown to produce significant cognitive and functional improvements with good effect sizes in past RCTs (ACTIVE) with up to 10 year durability and transfer of training to measures of self-reported everyday functioning; 3) provides a “cognitive treatment engine²⁸²” which alone has a very highly likelihood of yielding significant cognitive and functional improvements, enabling us to test the augmenting effects of tDCS; and 4) is computerized, well standardized, and efficiently implemented.

Combined CT. We selected a combined CT approach rather than testing one specific training task: 1) This would optimize CT treatment effects for this primary intervention, providing a strong and reliable engine of change with which to examine effects of tDCS; 2) This approach enables us to affect several related cognitive functions that are strongly dependent on neural plasticity of the frontal cortex; and 3) This approach would maximize participants interest and motivation versus a single task that could become boring.

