Aim 2. Determine critical tDCS current properties and specific brain regions associated with responder vs. non-responder to tDCS and CT intervention using machine learning.

H2.1. Current intensity and direction will significantly predict response vs. non-response to tDCS and CT intervention on the NIH Toolbox Fluid Cognition Composite Score (ACT primary outcome).

H2.2. Current intensity and direction within bilateral rostral middle frontal, right superior frontal and frontal pole, and left pars orbitalis regions will most strongly predict response vs. non-response to tDCS and CT intervention.

H2.3. Current intensity and direction will outperform clinical/demographic characteristics alone (e.g., age, sex, comorbidities, mental health, Alzheimer's disease risk, cognition, etc.) in predicting tDCS response.

Exploratory Aim. Evaluate computational methods for achieving precision delivery of dosing characteristics in tDCS.

HE.1. Adjusting tDCS current intensity input into computational models will achieve precision delivery of targeted dosing characteristics.

HE.2. Adjusting electrode locations input into computational models will achieve precision delivery of targeted dosing characteristics.

No new data will be collected from participants to achieve these aims. Only existing data collected with consent from participants in the course of the primary ACT study will be used. These data will be analyzed using advanced analytic methods (computational modeling and machine learning) to achieve all three aims specified in section 6.18.

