Aim 1. Dependent measures. The primary dependent measure in Aim 1 is current density computed in individual head models from existing MRIs. Current components will be further quantified as current intensity and direction. **Rationale.** Computed current density will provide an estimate of tDCS current dose within brain regions unique to each person's neuroanatomy. **Outcome analyses.** **H1.1.** The regression analysis between current density (dependent variable) and anatomical measures (independent variable) e.g., brain volume ratio, sulcus depth, bone thickness will test the hypothesis that unique current density distribution in each person is significantly affected by individual characteristics in neuroanatomy. **H1.2.** Current characteristics generated from models will be compared between inclusion and exclusion of white matter lesions. A false discovery rate (FDR)-corrected voxel-wise within participants analysis will test the hypothesis that inclusion of white matter lesions in computational models significantly alters current characteristic predictions.

Aim 2. Dependent measures. The primary dependent measure in Aim 2 is balanced accuracy. This measure provides an overall index of the performance to differentiate responders from non-responders. **Rationale.** By using this measure, we provide a single performance indicator upon which the **heterogeneity of response** in tDCS augmented CT can be revealed. Much of our preliminary data is based on analyses using this measure. **Outcome analyses.** All analyses will be conducted with the intent to optimize prediction of tDCS outcome. McNemar test at one-tailed 0.05 significance level will be conducted to determine whether current intensity and direction will outperform clinical and demographic characteristics alone in predicting tDCS response.

Exploratory Aim. Dependent measures. The primary dependent measure in the Exploratory Aim is log-likelihood distance measure. Adjustments of electric current intensity and electrodes placement in computational models will be used to minimize the log-likelihood distance measure to the Gaussian Mixture Model of the responders' current distribution.

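### Section 6.18, Aim 2: the McNemar test for H2.3 compares raw accuracy, but the declared primary measure is balanced accuracy

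*Combined protocol and SAP*

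**What the plan says.** The relevant text is in protocol section 6.18, the secondary machine-learning analysis of existing trial data.

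- **Measure.** For Aim 2, "The primary dependent measure in Aim 2 is balanced accuracy". Its role is explained in the next sentence: "This measure provides an overall index of the performance to differentiate responders from non-responders".
- **Hypothesis H2.3.** "Current intensity and direction will outperform clinical/demographic characteristics alone" in predicting response to tDCS.
- **Test.** The outcome-analysis paragraph for Aim 2 names one inferential procedure: "McNemar test at one-tailed 0.05 significance level will be conducted to determine whether current intensity and direction will outperform clinical and demographic characteristics alone". The label H2.3 is not printed beside it, but the wording is that of H2.3.
- **Response.** H2.1 ties response to the trial's primary outcome: "Current intensity and direction will significantly predict response vs. non-response to tDCS and CT intervention on the NIH Toolbox Fluid Cognition Composite Score". Section 6.18 gives no cut-off for response, no expected share of responders, no class balancing and no weighted form of the test.

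**The concern.** The measure and the test answer different questions. McNemar's test uses the participants whom only one of the two models classifies correctly, and its null hypothesis is equal overall accuracy. When one class is larger, that class dominates. Balanced accuracy is chosen to prevent exactly this.

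H2.3 could therefore be declared supported when the current model is no better, or is worse, on the declared measure. It could also be missed when the current model is truly better. If the two results conflict, the plan gives no rule for which one decides, and the choice would be made after the data are seen.

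**Working it through.** The plan states no sample size, power or accuracy figure for Aim 2, so there is nothing to reproduce. The check is algebra, one worked data set and a simulation.

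**1. What each quantity measures.** Let p be the responder share, and let dSens and dSpec be the differences (current minus clinical model) in sensitivity and specificity. Let b be the number of participants only the current model gets right, and c the number only the clinical model gets right.

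- McNemar tests (b − c)/n, which is the raw accuracy difference p·dSens + (1 − p)·dSpec.
- The declared measure differs by (dSens + dSpec)/2.

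The two are equal if p = 0.5, or at any p if dSens = dSpec. They can have opposite signs only if one model gains sensitivity while losing specificity.

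**2. Illustrative sample size.** Section 6.1 says "An initial cohort of 80 participants collected across the two sites will be assigned to one of four conditions", and section 6.2 says "In phase 1, each block will have two participants for each arm", so Phase 1 gives 80/4 = 20 on active tDCS with CT. Section 6.1 continues: "In Phase 2, the remaining 280 participants will be randomized to the two CT arms". Section 6.2 allocates these equally, which gives 280/2 = 140. The total is 160, assuming no dropout and that the training-control arms are dropped.

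**3. One data set.** Assume 20% responders: 32 responders and 128 non-responders.

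| | Responders correct | Non-responders correct | Raw accuracy | Balanced accuracy |
|---|---|---|---|---|
| Current | 10/32 | 115/128 | 125/160 = 0.781 | (0.3125 + 0.8984)/2 = 0.605 |
| Clinical | 19/32 | 96/128 | 115/160 = 0.719 | (0.5938 + 0.7500)/2 = 0.672 |

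With no offsetting discordance within a class, b = 115 − 96 = 19 and c = 19 − 10 = 9. The exact one-sided McNemar p is P(Bin(28, 0.5) ≥ 19) = 0.044. The test favours the current model, which is worse on the declared measure.

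The converse also occurs. If the current model gains 10 responders and loses 15 non-responders, balanced accuracy rises by (10/32 − 15/128)/2 = 0.098. Raw accuracy falls by 5/160 = 0.031, and McNemar p = 0.89.

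**4. Rejection rates.** The simulation used n = 160, errors independent within class, one-sided 5% and 40,000 replicates per cell. McNemar is the exact binomial test on discordant pairs. The comparator is z = (d1 + d0)/√(v1 + v0), where d1 and d0 are the within-class paired differences in proportion correct and v1 and v0 are their variances. Models are written sensitivity/specificity. Entries are the percentage of trials declaring the current model superior at 20/25/30/40/50% responders.

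| Scenario (current vs clinical) | True balanced-accuracy difference | McNemar | Stratified test |
|---|---|---|---|
| A: 0.50/0.80 vs 0.65/0.65 | 0 | 49/37/26/11/3.5 | about 5 |
| A2: 0.50/0.70 vs 0.60/0.60 | 0 | 25/20/15/8/3.7 | about 5 |
| A3: 0.55/0.65 vs 0.60/0.60 | 0 | 11/10/8/5.5/3.8 | about 5 |
| B: 0.80/0.60 vs 0.45/0.75 | +0.10 | 0.2/1/3/19/52 | 48/53/56/61/62 |
| B2: 0.75/0.65 vs 0.50/0.70 | +0.10 | 5/10/15/32/54 | 46/51/54/59/61 |
| C: 0.70/0.70 vs 0.60/0.60 | +0.10 | 54 throughout | 45/49/53/58/59 |
| D: 0.40/0.80 vs 0.65/0.65 | −0.05 | 33/20/11/2/0.2 | under 1 |

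The algebra explains the pattern. At 20% responders, the raw accuracy difference in A is 0.2(−0.15) + 0.8(0.15) = +0.09. In B it is 0.2(0.35) + 0.8(−0.15) = −0.05, and in D it is 0.2(−0.25) + 0.8(0.15) = +0.07.

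**5. Sensitivity to assumptions.** With n = 128 (20% dropout, assumed), McNemar gives 41/31/23/10/3.5 in A and 0.4/1/3/15/44 in B. With a within-class error correlation of 0.3 at n = 160, it gives 62/47/33/13/3 in A and 0.1/0.6/3/22/65 in B. The same figures hold for 50–80% responders with sensitivity and specificity swapped.

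**The case against.** McNemar's test is a standard way to compare two classifiers on the same participants, and the size of the problem depends on facts the plan does not give. A median split on the Fluid Cognition Composite would make the classes equal and remove the conflict. At 40% responders the false-support rates in A, A2 and A3 are only 11%, 8% and 5.5%. The large figures need 20–25% responders together with models at clearly different operating points. If both models were tuned to balanced accuracy, large opposing trade-offs would be less likely. The documents neither state nor exclude any of this. It limits how large the effect is likely to be, but it does not make the stated test match the stated measure.

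Part of the power gap has another cause. At 50% responders the two measures coincide, yet B still shows 52% against 62%. About 4 to 5 points of that comes from using the exact McNemar test, and section 6.18 does not say which form is meant. The asymptotic form does not remove the problem: it raises false support in A to 54% at 20% responders.

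The matched test also has a price. In C, where there is no conflict, its power at 20% responders is about 45%, against 54% for exact McNemar and 59% for the asymptotic form. This objection stands and belongs in the cost of the change.

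McNemar could be run separately in responders and non-responders, but the text does not say so. That would test sensitivity and specificity one at a time, not balanced accuracy.

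**Conclusion.** The concern holds. The mismatch follows from the definitions and does not depend on the simulation. Its size cannot be fixed from the documents, because neither response nor the responder share is defined. Under the assumptions above, with 20–30% responders and equal balanced accuracy, McNemar wrongly supports H2.3 in between 8% (mildest trade-off, 30% responders) and 49% (strongest trade-off, 20% responders) of trials, against a nominal 5%. In B, where the current model is better by 0.10, its power over the same shares is 0.2–3%, against 48–56% for the matched test. With equal classes the mismatch disappears.

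The effect is confined to H2.3 in a secondary analysis. The trial's primary tDCS comparison and its participants are not affected. The correction should be made, but it is not critical to the trial.

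**What to change.** Replace the McNemar sentence in section 6.18 with wording such as: *H2.3 will be tested one-sided at 0.05 on the paired difference in balanced accuracy (current minus clinical/demographic model), by a z-test on the averaged within-class paired differences or a class-stratified paired bootstrap. McNemar's test will be reported only as a secondary comparison of raw accuracy.* Choose one of the two methods in advance. Report the responder share and each model's sensitivity and specificity beside the result. State the definition of response before unblinding, since the class sizes depend on it.

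The cost is one sentence and a few lines of code, with no new data and no change to participation. The statistical cost is lower power when responders are few and both classes gain equally (scenario C).

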We will leverage existing multimodal neuroimaging and behavioral outcomes data from the ACT trial to 1) **elucidate mechanism of action** underlying response to tDCS treatment with CT, 2) **address heterogeneity of response** in tDCS augmented CT by determining how individual variation in the dose of electrical current delivered to the brain interacts with individual brain anatomical and lesion characteristics; and 3) **refine the intervention strategy** of tDCS paired with CT by evaluating computational methods for estimating precision delivery of targeted dosing characteristics to facilitate tDCS augmented outcomes. We will employ state of the art MRI-derived computational modeling and machine learning (ML) applied to existing data to 1) create precision individualized computational models of electrical current in the brain from tDCS for all 360 participants in ACT (based in T1 weighted images), 2) determine the characteristics of electrical current calculated from electric current models associated with trial outcomes, and 3) evaluate a computational method for calculating possible precision dosing of tDCS parameters for optimizing trial outcomes in older adults.

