To date, all prior trials of tDCS have applied a fixed dosing strategy (e.g., 2mA for 20 min with electrodes at F3/F4 [10-20 measurement system]) in attempts to enhance CT – including ACT. However, prior research demonstrates that individual variability in head and brain anatomy (e.g., degree of atrophy, skull thickness, etc.) significantly alters the spread and intensity of direct electrical current delivered to the brain person to person. The impact of individual variation in electrical current delivered to the brain for clinical outcomes has rarely been examined, and methods aimed at increasing stimulation effectiveness and optimizing readiness to learn are only now beginning to be explored. We will use advanced MRI-derived computational modeling of electrical current from existing MRIs to provide a means for accurately estimating individual differences in tDCS current delivery to the brain in the largest existing sample of participants undergoing tDCS (i.e., ACT) with multimodal neuroimaging data. When combined with state-of-the-art machine learning approaches and behavioral outcome data (only unblinded once ACT has completed all follow-up visits), precision models of tDCS current will be derived to identify critical stimulation dosing characteristics (e.g., current intensity, direction/path of current) in specific brain regions associated with response vs. non-response to tDCS and CT intervention. These data will not only provide much needed information for determining how individual participant characteristics impact tDCS efficacy, but will also serve as a foundation for future precision medicine applications of tDCS and CT to remediate cognitive decline in older adults and potentially prevent or alter the trajectory towards Alzheimer's disease.

Aim 1. Determine inter-individual variability in tDCS current distribution using MRI-derived finite element modeling.

H1.1. Variability in neuroanatomy (e.g. increased atrophy, sulcus depth, skull thickness, etc.) will significantly decrease current intensity and alter the pathway/direction of electrical current flow induced by tDCS in the brain.

H1.2. White matter lesions, as measured by white matter hyper-intensities on FLAIR imaging, will significantly decrease current intensity and significantly alter the direction of electrical current flow induced by tDCS.

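### The precision-dosing objective in section 6.18 measures closeness to responders only, so the distance can fall with no gain, or with a loss, in a head's predicted response

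*Combined protocol and SAP*

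**What the plan says.** Section 6.18 describes a secondary analysis of existing trial data. Its third stated task is to "evaluate a computational method for calculating possible precision dosing of tDCS parameters for optimizing trial outcomes in older adults".

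Under Dependent measures, it says: "The primary dependent measure in the Exploratory Aim is log-likelihood distance measure". What is varied is described as "Adjustments of electric current intensity and electrodes placement in computational models", and these adjustments "will be used to minimize the log-likelihood distance measure to the Gaussian Mixture Model of the responders' current distribution". No formula for the distance is given. The section also does not state the number of mixture components, which heads are adjusted, or when the search stops.

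Hypothesis HE.1 reads: "Adjusting tDCS current intensity input into computational models will achieve precision delivery of targeted dosing characteristics". HE.2 says the same of electrode location.

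Non-responders appear earlier in the section. Its introduction says that the models will identify dosing characteristics in "specific brain regions associated with response vs. non-response to tDCS and CT intervention". The Aim 2 measure is balanced accuracy: "This measure provides an overall index of the performance to differentiate responders from non-responders".

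**The concern.** The stated purpose is to optimise outcome. That asks whether a given current is more likely in a responder than in a non-responder. The written objective asks whether a head resembles a typical responder. The two questions have different answers wherever the groups overlap.

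Two consequences follow. First, if current has nothing to do with response, the responders' distribution is simply the population's. The search still returns a target for every head and the primary measure still improves. Second, if predicted response rises with a current feature, a head already above the responders' mode is pulled back towards it, to a lower predicted response.

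The distance alone reveals neither case. Section 6.18 presents its results as groundwork for later individualised stimulation, so the definition of the target is what others would carry forward.

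**Working it through.** The plan states no figure for this aim, so there is none to reproduce. What follows is an illustration.

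**Inputs from section 6.18.** The objective is distance to the responders' mixture model. Intensity and electrode placement are adjusted in models only. Head models are planned for all 360 participants, so non-responders' currents will exist.

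**Inputs assumed.** The documents give no responder cut-off, responder share p, size or direction of the current effect, or distance formula. I take one current feature, distributed N(d,1) in responders and N(0,1) in non-responders, with every head moved to the responder mode, x = d. I use p = 0.5 first and then vary p and d.

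**No relation (d = 0).** The responder density equals the population density. The distance falls for every head moved to the centre, and predicted response stays at 0.50.

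**Monotone relation.** Predicted response at x with p = 0.5 is 1/(1 + exp(−(d·x − d²/2))), which rises with x. Heads above d are lowered. These are half of the responders and a fraction Φ(−d) of the non-responders:

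share lowered = 0.5p + (1 − p)Φ(−d), with d = √2·Φ⁻¹(AUC).

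After the move every head has predicted response 1/(1 + exp(−d²/2)). Before it, the mean over all heads is p = 0.50.

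| AUC | d | Φ(−d) | Share lowered | Mean loss among those lowered | Mean predicted response, all heads |
|---|---|---|---|---|---|
| 0.60 | 0.36 | 0.36 | 0.25 + 0.5×0.36 = 43% | 0.07 | 0.50 → 0.52 |
| 0.70 | 0.74 | 0.23 | 0.25 + 0.5×0.23 = 36% | 0.12 | 0.50 → 0.57 |
| 0.80 | 1.19 | 0.12 | 0.25 + 0.5×0.12 = 31% | 0.14 | 0.50 → 0.67 |

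**Other responder shares and separations, same model.** The extremes over p = 0.2 to 0.7 and d = 0.2 to 2.0 are:
- p = 0.2, d = 2.0: 0.10 + 0.8×0.023 = 11.8%.
- p = 0.7, d = 0.2: 0.35 + 0.3×0.421 = 47.6%.

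**Other shapes, p = 0.5.**
- Two-component mixtures in which predicted response still rises with current: 23% to 67% of all heads lowered, and 30% to 72% of responders.
- Responder SD 0.5 against 1, d = 0.8, where the relation is no longer monotone: 24% of all heads and 36% of responders lowered.

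**The case against.** Several replies have force.

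- **The average improves.** In the model above, mean predicted response rises at every AUC. Non-responders go from 0.48, 0.44 and 0.36 to 0.52, 0.57 and 0.67, and responders do not fall on average. This stands: where current predicts response, the rule helps overall. The loss is confined to a subset of heads.
- **Non-responders do enter, through Aim 2.** This stands in part. A reader might infer that the method never uses non-responders' currents, but that is true only of the objective function, since Aim 2 may choose the features. Choosing features settles which coordinates are matched. It does not settle whether moving along them raises predicted response.
- **Which heads are adjusted, and how far, is not stated.** If only non-responders' models were adjusted, the share lowered among them would be 36%, 23% and 12%. A group-level match, or stopping once inside the responder range, would lower fewer. This limits the size, not the principle.
- **Distance fits HE.1 and HE.2.** Those hypotheses ask whether a target can be reached, and distance measures that. It does not measure the outcome purpose that the section also states.
- **Staying near observed responders is cautious.** This is a fair reason not to replace the objective. With equal variances the responder to non-responder log-likelihood ratio is linear in current and has no maximum, so optimising it would send heads to the sparse edge of the observed range.
- **It is exploratory and in silico.** Correct. Section 6.18 says that participation is unaffected, and no trial endpoint depends on this aim.

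**Conclusion.** The point holds in a limited form. The Exploratory Aim's objective contains no responder to non-responder contrast. A smaller distance is therefore not evidence of a better predicted outcome, and under a monotone relation it can accompany a worse one for a non-trivial share of heads while the average rises.

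The sizes of 43%, 36% and 31% rest on assumptions absent from the documents: equal-variance normals, half responders, and every head moved to the responder mode. Varying responder share and separation gives about 12% to 48%, and mixtures differ further.

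A reader might infer that about a third of heads, and half of all responders, are always made worse. The documents do not support that. One third needs particular pairs of p and d, such as p = 0.5 with d = 0.97. One half needs a single symmetric distribution with every responder's head adjusted, whereas the plan names a mixture and does not say which heads are adjusted. Nor do the documents support a claim that the rule is harmful on average.

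**What to change.** Keep the responder-distance objective and add three statements to the Exploratory Aim in section 6.18:

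1. For each adjusted head, report predicted response before and after adjustment. Take it from an Aim 2 model that outputs a probability, or from mixture models fitted to responders' and non-responders' currents in the existing data. Aim 2 as written promises only balanced accuracy, so the probability output must be specified.
2. Count an adjustment as a precision-dosing gain only if predicted response does not fall. Report the share of heads in which it does fall.
3. If Aim 2 balanced accuracy does not exceed chance, report that no outcome-based target is supported.

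A likelihood-ratio objective restricted to currents observed in the trial can be a sensitivity analysis. It should not be the main objective, because of its behaviour at the edge of the data.

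The cost is a few sentences and one extra model fit on data already planned. The summary may look less favourable than the distance alone. The change concerns computation and reporting only, and proposes no dose.
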